6.2 IMPORTANT PROTOCOL DEVIATIONS

Handling of iPDS in analysis is included in the DV domain specifications and stored within the TMF in EDMS (2).

In addition, all COVID-19 related protocol deviations, regardless of important or non-important PDs will be included in the DV domain as well.

6.3 SUBJECT SETS ANALYSED

The following analysis set will be defined for this trial:

- **Enrolled Set (ES):**
This patient set includes all patients who signed informed consent. It will be used for analyses of patient disposition.
- **Treated Set (TS):**
This patient set includes all patients who received at least one dose of study drug. It will be used for all other analyses.

6.5 POOLING OF CENTRES

All patients from all centres will be pooled for descriptive analyses.

6.6 HANDLING OF MISSING DATA AND OUTLIERS

Safety data

The original results (OR) approach implies the presentation of data exactly as observed (not using time windows and not setting values to missing)

For safety data not by visit such as AE and possibly clinically significant laboratory abnormalities, OR approach will be used for the descriptive reporting for corresponding treatment periods.

The only exceptions where imputation might be necessary for safety evaluation are AE dates and AE start time and, start and stop dates for concomitant medications.

Missing or incomplete AE dates are imputed according to BI standards (4).

Partial start and stop dates for concomitant medications and historical medication use will be imputed to enable subsequent calculation (but not for display) by the following "worst case" approach:

- If the day of the end date is missing, then the end date is set to last day of the month (or to the patient's trial completion date, if it is earlier than the last day of the month).
- If the day and month of the end date are missing then the end date is set to 31st of December of the year (or to the patient's trial completion date, if it is earlier than the 31st of December of the year).

- If the day of the start date is missing then the start date is set to first day of the month (except for escape medication, where the first dosing day will be used if first dosing happened in the same month).
- If the day and month of the start date are missing then the start date is set to 1st January of the year.
- All other cases need to be assessed by the trial team on an individual basis, using the above points as guidance.

If a concomitant medication is ticked to be ongoing, it is expected that the end date is missing and will not be imputed for display purposes.

Time since first diagnosis

For incomplete information on the date of first diagnosis, time since first diagnosis will be calculated as follows:

- If the year of first diagnosis is unknown, time since first diagnosis will be set to missing.
- If day and month of the first diagnosis are unknown, time since first diagnosis will be calculated as if diagnosed on the 30th of June of that year.
- If only the day of the first diagnosis is unknown, time since first diagnosis will be calculated as if diagnosed on the 15th of that month.

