7.1 DEMOGRAPHIC AND OTHER BASELINE CHARACTERISTICS

Only descriptive statistics are planned for this section of the report:

Sex, ethnicity, race, age, height, weight, BMI, mutation status of the IL36RN, CARD14 and AP1S3, disease characteristics for current flare, time since first diagnosis.

Age [years] will be determined as the difference between year of birth and year of informed consent. BMI will be calculated as weight [kg] / height [m]²

Medical History for GPP includes mutation status (IL36RN, CARD14 and AP1S3), as well as the details, if any, on the presence of chronic plaque psoriasis or chronic erythrodermic psoriasis will be summarized. The method by which diagnosis of GPP was confirmed is also collected.

Disease characteristics will include details on current flare.

Time since first diagnosis [years] will be calculated as the difference between date of first diagnosis and date of informed consent, divided by 365.25.

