7.2 CONCOMITANT DISEASES AND MEDICATION

Only descriptive statistics are planned for this section of the report.

Concomitant diseases (i.e. baseline conditions) and concomitant non-drug therapies will be coded according to the most recent version of MedDRA. Concomitant medications will be coded according to the most recent version of the World Health Organisation – Drug Dictionary.

A medication/non-drug therapy will be considered concomitant to treatment, if it

- is ongoing at the start of that treatment period or
- starts within that treatment period (see [Section 6.1](#) for the definition).

A medication/non-drug therapy will be considered as prior medication/non-drug therapy, if the end date of the medication/therapy is at any time prior to the start of that treatment period.

Concomitant medication use will be summarized with frequency and percentage of patients by Anatomical Therapeutic Chemical 3 (ATC3) class and preferred name.

Concomitant use of non-drug therapies will be summarised with frequency and percentage.

Historical medication for GPP will be summarised with frequency and percentage of patients, including presentation by type of historical medication (preferred name), and by reason for discontinuation.

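### SAP 6.6 does not cap an imputed first-diagnosis date at informed consent, so time since diagnosis can come out negative; its end-date rule for historical medication has a related, conditional gap

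*SAP*

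**What the plan says.** **Diagnosis date.** SAP 6.6 has three rules. If the year is unknown, the duration is set to missing. If day and month are unknown, "time since first diagnosis will be calculated as if diagnosed on the 30th of June of that year". If only the day is unknown, "time since first diagnosis will be calculated as if diagnosed on the 15th of that month". SAP 7.1 defines the duration in years as the "difference between date of first diagnosis and date of informed consent, divided by 365.25".

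**Medication dates.** SAP 6.6 states that "Partial start and stop dates for concomitant medications and historical medication use will be imputed to enable subsequent calculation", under an approach it labels worst case. A stop date without a day moves to the end of the month. Without day and month, "the end date is set to 31st of December of the year". Both are limited only by the patient's trial completion date if that is earlier.

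**Classification.** SAP 7.2 counts a medication as concomitant if it "is ongoing at the start of that treatment period" or starts within that period, and as prior if its end date precedes the start of the period. Historical GPP medication also has its own summary there, by preferred name and by reason for discontinuation.

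**The concern.** First diagnosis should not fall after consent in a program that enrols patients because they have the disease. Yet the imputation uses a fixed calendar day and does not look at the consent date. When diagnosis and consent share the year or month, the fixed day can fall after consent and the duration becomes negative. SAP 7 includes the minimum among the summary statistics for its tables, so one such patient would be enough to print an impossible value in the baseline table.

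The medication rule has the same structure: it moves a partial stop date forward without looking at first dose. For a drug recorded as concomitant, that is a reasonable conservative choice. For a drug recorded as already stopped, it can contradict the record. At stake are the accuracy of one baseline variable and, conditionally, of the concomitant-medication table.

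**Working it through.** The plan gives no figure on this point, so there is none to reproduce. The check applies the SAP rules to illustrative dates in a 365-day year (2023).

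**1. Diagnosis, year only known, same year as consent**

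Inputs: imputed date 30 June (SAP 6.6); reference date informed consent, divisor 365.25 (SAP 7.1). SAP 7.1 does not fix the order of subtraction; consent minus diagnosis is used, since it gives positive values in ordinary cases.

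Duration = (consent date - imputed diagnosis date) / 365.25.

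- Consent 15 March 2023: -107 / 365.25 = -0.29 years. A patient diagnosed in 2023 before that consent has a true duration between 0 and 73 days (1 January to 15 March), so -107 days is outside the possible range.
- Earliest case, consent 1 January: -180 / 365.25 = -0.49 years.
- The result is negative for every consent date from 1 January to 29 June, which is 180 of 365 dates.

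The share of affected patients is not simply 180/365, because diagnosis must come before consent, and that makes later consent dates more likely. Assume both dates are uniform over the year, conditional on diagnosis before consent. Then:

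P(consent before 30 June) = (180/365)² = 0.243, about 24%.

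This is the share among same-year, year-only cases, not among all patients.

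**2. Diagnosis, day unknown, same month as consent**

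The imputed date is the 15th, so consent on days 1 to 14 gives a negative value.

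- Consent 3 March: -12 / 365.25 = -0.03 years.
- Earliest case, consent on the 1st: -14 / 365.25 = -0.04 years.

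**3. Effect of a cap at consent**

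Duration = (consent - min(imputed date, consent)) / 365.25. Over all 365 consent dates in the year-only case, no value is negative and the minimum is 0.

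**4. Historical medication, if classified under SAP 7.2**

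Assumptions: one dose; completion 112 days later (16 weeks after last dose, Protocol 5.2.4.2.1); partial stop date in the year or month of first dose.

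Imputed end = min(end of year or month, first dose + 112 days).

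With first dose on 10 March 2023, completion is 30 June 2023:

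| Recorded stop | Imputed end | Status under SAP 7.2 |
|---|---|---|
| 2023 | 30 June 2023 | concomitant |
| March 2023 | 31 March 2023 | concomitant |

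Both results hold even if the drug was known to have stopped before 10 March. Neither bound can fall before first dose, so the imputed end is on or after first dose for all 365 possible first-dose dates. With a cap at the day before first dose, the count is 0 of 365.

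**5. Other text that might prevent this**

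- The only mention of first dosing in SAP 6.6 concerns start dates of escape medication.
- Individual assessment by the trial team is for cases that the listed rules do not cover.
- The sponsor's standard for incomplete dates is cited in that section for AE dates only.
- Protocol inclusion criterion 1 sets no minimum time since diagnosis.

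**The case against.** The diagnosis case is narrow. It needs a diagnosis in the year or month of consent and an incomplete date, and recent diagnoses are probably the ones most often dated in full (an assumption; the documents give no frequency). The reference in inclusion criterion 1 to relapsing or persistent disease makes a same-month diagnosis less likely. A negative duration is also easy to spot at data review. All of this limits the size of the problem, but the rule still gives an impossible value, and a correction made at review would be ad hoc.

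The objection to the medication half is stronger. SAP 7.2 summarises historical GPP medication separately, and Protocol 8.3.1 lists medication history and concomitant therapy as separate source items. Nothing states that historical records feed the concomitant table. The worst-case direction is declared and is stated to be for calculation, not display. This stands: the medication half is conditional. What remains is that SAP 6.6 names historical use within the scope of the rule, and the SAP 7.2 definitions do not exclude those records.

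A reader might infer that background therapy during spesolimab is overstated and that this distorts the reading of adverse events. The documents do not support that. The record flow is not stated, and no planned AE analysis in SAP 7.8 adjusts for or conditions on concomitant medication. A reader might also take the late imputed end date to mean that use is counted through the whole follow-up. SAP 7.2 plans only frequencies and percentages of patients, with no duration of use, so only a yes/no flag could change.

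**Conclusion.** The diagnosis point holds as a minor defect. As written, SAP 6.6 and 7.1 together can give a negative time since diagnosis, to about -0.49 years with year only and about -0.04 years with day unknown. The documents do not allow an estimate of how many patients are affected. The 24% rests on both dates being uniform and applies only to same-year, year-only cases. A figure of 49% (180/365) is tempting, but it ignores that diagnosis precedes consent.

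The medication point holds only if historical records enter the SAP 7.2 classification, which the SAP leaves open. In that case a drug recorded as stopped, with a partial stop date in the month or year of dosing, could be flagged as concomitant.

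Both parts affect descriptive baseline and medication tables only. The TEAE, SAE and AESI results are unchanged.

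**What to change.** In SAP 6.6:

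1. **First diagnosis:** use the earlier of the imputed date and the date of informed consent. The capped value is 0, the lower edge of the possible range, so it is approximate but never impossible.
2. **Medication recorded as stopped before a flare treatment period:** cap the imputed end date at the day before the first dose of that period, and do not let it fall before the drug's own start date. The cap has to be tied to the period, because patients may re-enter for later flares and SAP 7.2 classifies by treatment period. A single cap at the first-ever dose could place the end of a drug used between flares before its start.
3. **Medication recorded as concomitant:** keep the worst-case rule.

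If historical GPP records are not meant to enter the prior/concomitant classification, one sentence in SAP 7.2 saying so would settle the medication point instead.

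The cost is two clauses and minor programming. No new data are needed.

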7. PLANNED ANALYSIS

For End-Of-Text (EoT) tables, the set of summary statistics is N / Mean / SD / Min / Q1 / Median / Q3 / Max.

For tables that are provided for endpoints with some extreme data, median, quartiles and percentiles should be preferred to mean, standard deviation, minimum and maximum.

Tabulations of frequencies for categorical data will include all possible categories and will display the number of observations in a category as well as the percentage (%) relative to the respective treatment group (unless otherwise specified, all patients in the respective patient set whether they have non-missing values or not).

The precision for percentages should be one decimal point, unless the denominator is smaller than 100 (in all treatment columns), in which case percentages are given in integer numbers. The category “missing” will be displayed only if there are actually missing values.

Disposition of the patient population participating in the trial will be summarised by the presentation of the frequency of patients enrolled, enrolled but not treated, enrolled and treated, who completed participation in the trial, and who were prematurely discontinued from trial, by reason. The iPDS, baseline conditions/medical history, demographic/baseline characteristics, concomitant medications, concomitant non-drug therapies, exposure will be presented based on TS for the entire trial duration. In addition, the number of flares will also be summarized based on TS.

For safety data, per patient analysis based on patient will be used for the analysis, whose denominator will be the number of patients or time at risk per patient for all applicable periods.

7.1 DEMOGRAPHIC AND OTHER BASELINE CHARACTERISTICS

Only descriptive statistics are planned for this section of the report:

Sex, ethnicity, race, age, height, weight, BMI, mutation status of the IL36RN, CARD14 and AP1S3, disease characteristics for current flare, time since first diagnosis.

Age [years] will be determined as the difference between year of birth and year of informed consent. BMI will be calculated as weight [kg] / height [m]²

Medical History for GPP includes mutation status (IL36RN, CARD14 and AP1S3), as well as the details, if any, on the presence of chronic plaque psoriasis or chronic erythrodermic psoriasis will be summarized. The method by which diagnosis of GPP was confirmed is also collected.

Disease characteristics will include details on current flare.

Time since first diagnosis [years] will be calculated as the difference between date of first diagnosis and date of informed consent, divided by 365.25.

7.2 CONCOMITANT DISEASES AND MEDICATION

Only descriptive statistics are planned for this section of the report.

Concomitant diseases (i.e. baseline conditions) and concomitant non-drug therapies will be coded according to the most recent version of MedDRA. Concomitant medications will be coded according to the most recent version of the World Health Organisation – Drug Dictionary.

A medication/non-drug therapy will be considered concomitant to treatment, if it

- is ongoing at the start of that treatment period or
- starts within that treatment period (see [Section 6.1](#) for the definition).

A medication/non-drug therapy will be considered as prior medication/non-drug therapy, if the end date of the medication/therapy is at any time prior to the start of that treatment period.

Concomitant medication use will be summarized with frequency and percentage of patients by Anatomical Therapeutic Chemical 3 (ATC3) class and preferred name.

Concomitant use of non-drug therapies will be summarised with frequency and percentage.

Historical medication for GPP will be summarised with frequency and percentage of patients, including presentation by type of historical medication (preferred name), and by reason for discontinuation.

7.3 TREATMENT COMPLIANCE

Not applicable.

7.4 PRIMARY ENDPOINT(S)

Refer to [section 7.8.1](#) for the description of adverse events including the primary endpoint.

7.5 SECONDARY ENDPOINT(S)

Refer to [section 7.8.1](#) for the description of adverse events including the secondary endpoint.

7.7 EXTENT OF EXPOSURE

Treatment exposure is defined as the total dose of randomized spesolimab [mg] received per patient. In general, the total dose of spesolimab [mg] received per [REDACTED] is calculated as the

total [REDACTED] volume [mL], as documented on the eCRF, times the strength prepared in the [REDACTED]

Strength in [REDACTED]
[REDACTED]

The duration of the [REDACTED] trial treatment [minutes] at each visit will be calculated as the end of the [REDACTED] date/time minus the start of the [REDACTED] date/time.

The number of doses will be calculated, which is based upon the number of visits at which doses of study drug were administered.

Time at risk will be assessed in months per definition in [Section 7.8.1](#), where the end date will be the end of each flare treatment period in [Table 6.1: 1](#).

The duration of [REDACTED], the number of doses, time at risk and the total dose [mg] will be summarised by descriptive statistics (N, mean, SD, minimum, Q1, median, Q3, maximum), using per patient analysis for all flare treatment period.

7.8 SAFETY ANALYSIS

All safety analyses will be performed following BI standards. No hypothesis testing is planned.

For all flare treatment period (all flares for a patient combined) based on TS, the AE data and possibly clinically significant laboratory abnormalities will be analysed under OR (as defined in [Section 6.6](#))

7.8.1 Adverse Events

AEs will be coded with the most recent version of MedDRA. Patients will be analyzed according to the actual treatment received.

The analysis of AEs will be based on the concept of treatment emergent AEs. This means that all AEs will be assigned to the screening phase, treatment phase or follow-up phase as defined in [Section 6.1](#). Since only the start date of an AE is collected (without start time), any AE occurrence on the same day as spesolimab at Day 1 will be assigned to the on-treatment period.

The primary endpoint of occurrence of treatment emergent adverse events (TEAE), will be analysed as the exposure-adjusted adverse event incidence rates in all flare treatment period based on TS by using per patient analysis for TEAE.

Per patient analysis for TEAE

- 1) The exposure adjusted incidence rate (per 100 patient years) of a selected treatment emergent adverse event is defined as the number of patients experiencing the adverse event per treatment group during time at risk divided by the total time of patients at risk in that treatment group to contribute the event to the analysis multiplied by 100 (per 100 patient years).

Time at risk [patient years] = (date of onset of AE – first treatment start date within that treatment period + 1) / 365.25

For all flare treatment period on a patient level, each flare treatment period is combined with the previous flare treatment period as defined in [Section 6.1](#).

- 2) If, for a patient, the selected treatment emergent adverse event didn't occur during the above defined treatment period (per [Section 6.1](#)) then the time at risk will be censored at the earliest of date of death, last contact date per EoS page, or the end of the above defined treatment period.

For each selected treatment emergent AE, the exposure adjusted incidence rate will be calculated as:

Incidence rate [1/100 Patient years (pt-yrs)] = 100 * number of patients with TEAE / Total TEAE-specific time at risk [patient years].

The analyses of AEs will be descriptive in nature. All analyses of AEs will be based on the exposure adjusted incidence rates (per 100 patient years or per 100 flare treatment period years), as well as the number of patients with AEs and the number of flare treatment periods with AEs. System organ classes (SOCs) (if applicable) will be sorted according to the standard sort order specified by the European Medicines Agency (EMA), preferred terms (PTs) (if applicable) will be sorted by total frequency (within SOC).

For further details on summarization of AE data, please refer to "Handling and summarization of adverse event data for clinical trial reports and integrated summaries" ([3](#)) and "Handling of missing and incomplete AE dates" ([4](#)).

An overall summary of AEs will be described in all flare treatment period based on TS by per patient analysis. The exposure-adjusted incidence rate and frequency will be summarized by treatment, primary SOC and PT for the following AEs: drug-related AEs considered by the investigator, AEs leading to treatment discontinuation, other significant AEs, SAEs, drug-related SAEs, AESIs, and user-defined adverse event categories (UDAEC) and serious UDAEC (cf. [Table 7.8.1: 1](#)). AEs will also be summarized by the maximum intensity.

According to ICH E3 ([5](#)), the sponsor has defined AEs which are to be classified as ‘other significant’. For the current trial, these will include those non-serious AEs which were reported with ‘action taken = Drug Withdrawn’ or ‘action taken = Dose Reduced’.

The following are considered as AESIs (see Sec 5.2.4.1.4 of CTP):

- Potential Severe Drug Induced Liver Injury (DILI)
- Systemic hypersensitivity reactions including [REDACTED] reactions and anaphylactic reaction
- Severe infections (according to RCTC grading in the ISF)
- Opportunistic and mycobacterium tuberculosis infections
- Peripheral neuropathy

The investigator identified AESI will be captured from the eCRF and reported as “Investigator reported AESI” table. In addition, user defined adverse event concepts (UDAEC) identified through specific search criteria will be reported separately ([Table 7.8.1: 1](#)).

For disclosure of AE data on ClinicalTrials.gov, the frequency of subjects with non-serious AEs occurring with an incidence of greater than 5% (in preferred terms) will be summarized by treatment, primary system organ class and preferred term. The frequency of subjects with SAEs will also be summarized.

Table 7.8.1: 1 Project MedDRA search criteria for User Defined Adverse Event Categories

User-defined AE category		
	Label	Description
Infections (serious/severe, opportunistic)	Infections ALL	Combined search strategy based on the individual UDAECs described below; the UDAEC “severe infections (investigator-defined) will be disregarded for this search
	Opportunistic infections	Narrow SMQ “Opportunistic infections”
	Tuberculosis infections	BIcMQ “Infections”: Narrow sub-search 8.2 “Tuberculosis related terms”
	Serious infections	all serious events in SOC “Infections and infestations”
	Severe infections	all events in SOC “Infections and infestations” of at least severe RCTC grade, by HLGT
Hypersensitivity	Hypersensitivity ALL	Combined search strategy based on the individual UDAECs described below
	Anaphylactic reaction	Narrow SMQ “Anaphylactic reaction”
	Angioedema	Narrow SMQ “Angioedema”
	Hypersensitivity	Narrow SMQ “Hypersensitivity”
	DRESS, algorithmic	
Based on broad SMQ “Drug reaction with eosinophilia and systemic symptoms” (SMQ code 20000225), defined using algorithm as follows:
 
A or (B and C and D) or (B and C and E) or (B and D and E)
 
where the categories A, B, C, D and E are defined categorisations of the PTs of the SMQ. For PTs of category A only narrow scope is used, for all other categories broad scope is used.
 
For identification of potential DRESS through the combination of adverse event occurrences within each of the categories B, C, D and E, adverse event start and end dates will be used. For the latter, potential DRESS is then identified if, within a 7-day period after occurrence of a relevant contributing event (assessed on each day between start and end date [inclusive] of the initiating event), there is at least one adverse event reported (based on start date only) from each of the other applicable categories within a specific combination of categories as described above (in parentheses).
 
If the end date is missing, the event is considered to be ongoing, and end date will be the last day of the applicable treatment period

	DRESS, narrow	Narrow SMQ “Drug reaction with eosinophilia and systemic symptoms”, any event within category A only

Malignancies	Malignant tumours	Narrow Sub-SMQ "Malignant tumours" Narrow Sub-SMQ "Haematological malignant tumours" Narrow Sub-SMQ "Non-Haematological malignant tumours"
	Malignant skin tumours	Broad Sub-SMQ "Skin malignant tumours"
	Skin melanomas	HLT Skin melanomas (excl. Ocular)
	Non-melanoma skin cancer (NMSC)	Broad Sub-SMQ "Skin malignant tumours" excluding HLT Skin melanomas (excl. Ocular)
	Malignancies excluding NMSC	Sub-SMQ "Malignant tumours" excluding NMSC, whereas NMSC is defined above
3-point MACE	3-point MACE	BIcMQ "Major Adverse Cardiovascular Events" with Narrow sub-search 1.1 "3-Point MACE (part 1/2)" Narrow sub-search 1.2 "3-Point MACE (part 2/2)"**
Torsades de Pointes	Torsades de Pointes	Broad sub-SMQ "Torsade de pointes/QT prolongation"
Peripheral neuropathy	Peripheral neuropathy	Narrow SMQ "Demyelination" Narrow SMQ "Guillain-Barre syndrome" Narrow SMQ "Peripheral neuropathy"

*this is achieved by retrieving all cases found either by running subsearch 1 in narrow scope (BIcMQ search ID 32019093) or subsearch 2 (BIcMQ serach ID 32019094

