5.2.4.2 Adverse event collection and reporting

5.2.4.2.1 AE Collection

The investigator shall maintain and keep detailed records of all AEs in the patient files. The following must be collected and documented on the appropriate CRF(s) by the investigator:

- From signing the informed consent onwards until the individual patient's end of program (16 weeks after last dose of spesolimab, or at the time of withdrawal of participation): all AEs (serious and non-serious) and all AESIs.
- After the individual patient's end of program: the investigator does not need to actively monitor the patient for new AEs but should only report any occurrence of cancer and program drug-related SAEs and program drug-related AESIs of which the investigator may become aware of by any means of communication, e.g. phone call. Those AEs should however not be reported in the CRF.
- Upon patient re-entry into the program, the patient should be re-evaluated to ensure that eligibility criteria are still met and the overall program is still running in order to assess AEs (serious and non-serious) and AESIs.

Vital Status Data Collection

Patients who withdraw their consent to program participation, who agree to be contacted further but do not agree to physical visits, should be followed up as described in section [3.2.4.2](#), withdrawal from program treatment. Thus, for patients who withdraw their consent

but agree to be contacted by phone for a last follow-up assessment at 16 weeks after last drug intake, the investigator must report any occurrence of cancer, all deaths / fatal AEs regardless of relationship, and program drug-related SAEs and and program drug-related AESIs the investigator becomes aware of.

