7.1.1 Safety analyses

In general, safety analyses will be descriptive in nature and will be based on BI standards. No hypothesis testing is planned.

Adverse events will be coded using the Medical Dictionary for Drug Regulatory Activities (MedDRA). Standard BI summary tables and listings will be produced. Statistical analysis and reporting of adverse events will concentrate on treatment-emergent adverse events, i.e. all adverse events occurring between start of treatment and end of the REP, a period of 16 weeks after the last dose of program medication. Adverse events that start before first drug intake and deteriorate under treatment will also be considered as 'treatment-emergent'. All adverse events with an onset between start of treatment and end of the REP, a period of 16 weeks after the last dose of program medication, will be assigned to the on-treatment period for evaluation.

All treated patients will be included in the safety analysis.

Frequency, severity, and causal relationship of adverse events will be tabulated by system organ class and preferred term. after coding according to the current version of the Medical Dictionary for Drug Regulatory Activities (MedDRA) at database lock.

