4. CHANGES IN THE PLANNED ANALYSIS OF THE STUDY

Not applicable.

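### The SAP has no rule for adverse events that begin before the first dose and worsen after it, which the protocol counts as treatment-emergent

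*SAP*

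**What the plan says.** **Protocol 7.1.1** gives two routes to treatment-emergent status. The first is by onset, and such events go to the on-treatment period: "All adverse events with an onset between start of treatment and end of the REP, a period of 16 weeks after the last dose". The second is by worsening, and the sentence that adds these events to the treatment-emergent ones begins: "Adverse events that start before first drug intake and deteriorate under treatment will also be considered as".

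**Protocol 5.2.4.2.1** has AEs collected "From signing the informed consent onwards until the individual patient" reaches the end of the program. Events between consent and first dose are therefore in the database as AEs.

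**SAP 7.8.1** says it uses the concept of treatment-emergent AEs and then explains it by pointing to the phases of Section 6.1: "all AEs will be assigned to the screening phase, treatment phase or follow-up phase as defined in". It notes that AE start times are not collected and settles the tie on the dosing day: "any AE occurrence on the same day as spesolimab at Day 1 will be assigned to the on-treatment period".

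**SAP Table 6.1: 1** ends the screening phase one minute before the Day 1 dose and starts the treatment phase at that dose. **SAP 7.4 and 7.5** send the primary and secondary endpoints to 7.8.1. Under "CHANGES IN THE PLANNED ANALYSIS OF THE STUDY" (Section 4), the SAP enters that nothing applies.

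**The concern.** The SAP presents phase assignment as the meaning of treatment-emergent, and none of its visible text mentions worsening. An analyst who follows it would leave a pre-dose AE in the screening phase whatever happened to it after spesolimab. The protocol says the opposite, and the SAP does not declare the difference.

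The same assignment drives all three endpoints: TEAEs, treatment-emergent SAEs and treatment-emergent AESIs. Patients enter during an active flare, which protocol 1.1 describes as able to deteriorate quickly, so worsening soon after dosing is plausible. Safety is the only unredacted endpoint domain in this program. One event that becomes serious or severe after dosing matters to the reader of the tables even though nothing is tested.

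**Working it through.** **1. The two rules side by side**

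| AE history | Protocol 7.1.1 | SAP 6.1 / 7.8.1 |
|---|---|---|
| Starts on or after the Day 1 date, within 16 weeks (16 × 7 = 112 days) of the last dose, no re-screening | Treatment-emergent, except that an event earlier on Day 1 than the dose qualifies only if it worsens | On-treatment |
| Starts before the Day 1 date, does not worsen | Not treatment-emergent | Screening |
| Starts before the Day 1 date, worsens after dosing, one record | Treatment-emergent | Screening |

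The residual period agrees (16 weeks and 112 days). The third row is the conflict.

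**2. Can the SAP formula take such an event?**

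SAP 7.8.1 sets time at risk in years to (AE onset date − first treatment start date + 1) / 365.25. With the recorded pre-dose start date:

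| Onset relative to the dosing date | Days at risk | Years |
|---|---|---|
| 4 days before | −4 + 1 = −3 | −0.008 |
| 2 days before | −2 + 1 = −1 | −0.003 |
| 1 day before | −1 + 1 = 0 | 0 |
| Same day | 0 + 1 = 1 | 0.003 |

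The formula works only from the dosing date onwards. To apply the protocol's second route, the programmer would have to supply a different onset date, and the SAP names none.

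**3. Who is exposed?**

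- The AE must start after consent and before the calendar day of first dosing. The flow chart allows Visits 1 and 2 on the same day, and protocol 6.1.1 lets dosing follow eligibility at once, so for many patients this window may be empty.
- The event must remain one record. Protocol 5.2.4.1.1 makes worsening of underlying disease or of pre-existing conditions an AE in its own right. SAP 7.8.2 to 7.8.4 treat relevant laboratory, vital-sign and ECG findings at screening as baseline conditions. Worsening of any of these after dosing gives a new AE with a post-dose onset, which the SAP counts.
- What remains is a new clinical AE that arose after consent. Protocol 6.1.3 asks for changes to AEs already reported to be recorded at each visit, but nothing visible requires a new record.

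**4. Size, by illustration only**

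The documents give no count of such events and no planned number of patients. Assumptions: 113 days at risk without the event (112 + 1, single dose); 3 patients already counted, each at day 14 of risk; one worsened event added at day 8 of risk; N = 10, 20 or 50.

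Rate before = 100 × 3 / {[(N − 3) × 113 + 3 × 14] / 365.25}

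Rate after = 100 × 4 / {[(N − 4) × 113 + 3 × 14 + 8] / 365.25}

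For N = 20, before: 17 × 113 + 42 = 1,963 days = 5.374 years, and 300 / 5.374 = 55.8. After: 16 × 113 + 50 = 1,858 days = 5.087 years, and 400 / 5.087 = 78.6.

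| N | Frequency | Rate per 100 patient-years |
|---|---|---|
| 10 | 30% to 40% | 131.5 to 200.7 |
| 20 | 15% to 20% | 55.8 to 78.6 |
| 50 | 6% to 8% | 20.5 to 27.8 |

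These figures show the effect of one event on one row of a table. They do not show how often it would happen.

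**The case against.** The best defence is that silence is not removal. The SAP elaborates protocol Section 7 and assumes the reader knows it. Protocol 7.1.1 itself sets the onset rule beside the worsening rule, so restating one need not cancel the other. Safety analyses follow sponsor standards that are not among the documents and may contain the rule.

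Part of this stands: it cannot be shown that the final programs will omit these events. It does not remove the conflict. SAP 7.8.1 says what the concept means, cites the standards only for further detail on summarization and incomplete dates, and gives a formula that cannot process the events.

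A reader might infer more than the documents support:

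- **That all three endpoints are materially biased downwards.** The overall primary result counts patients with any TEAE. In the earlier randomized trial 91.4% of spesolimab patients had an AE by week 12 (protocol 1.2.3), so a patient who loses one worsened event would usually still count through another. The Day 1 tie rule also pushes the other way.
- **That pre-dose infections turning severe, or sepsis, are typical cases.** Exclusion criteria 3 to 5 remove many pre-dose infections and criterion 8 removes immediately life-threatening flares needing intensive care.
- **That re-entering patients lose events by the same mechanism.** An AE that starts in re-screening within 16 weeks of the last dose already meets the protocol's onset rule. Its loss comes from Table 6.1: 1, which closes the on-treatment period when the next screening begins. That is a separate issue.

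**Conclusion.** The conflict is real and undeclared: for one defined group of AEs the SAP as written gives a different classification from the protocol. The group is AEs that start after consent and before the day of first dosing, are kept as one record, and worsen after dosing. They would be missing from the TEAE, treatment-emergent SAE and AESI tables.

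The number is unknown and probably small. The effect lies mainly in single SAE, AESI and preferred-term rows, where one event can turn 0 into 1, and rarely in the overall any-TEAE result. The conclusion rests on the visible SAP text; an unseen sponsor standard or CRF completion guide could already close the gap in practice. The SAP should be amended, but the point does not undermine this descriptive analysis.

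**What to change.** Add to SAP 6.1 and 7.8.1: an AE with onset before first dosing whose intensity or seriousness increases after the start of spesolimab is treatment-emergent, and the date of worsening serves as its onset date for phase assignment and time at risk. Have sites record that date, for example by opening a new AE record when the event worsens. With a new record, the existing onset-based assignment already captures the event. If the sponsor prefers the onset-only rule, SAP Section 4 should declare it as a departure from protocol 7.1.1.

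The cost is a few lines of SAP text, a small derivation and one instruction to sites. Reported rates may rise slightly. The SAP also covers two other trials in the Expanded Access Program, so the wording should be checked against their protocols, which are not among the documents reviewed.
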